### **6.3.1.2. TEAEs by System Organ Class and Preferred Term**

The following summary tables of TEAEs will be provided by SOC (in internationally agreed order) and PT using frequency counts and percentages (i.e., number and percentage of subjects with an event):

- All unsolicited TEAEs
- All unsolicited TEAEs that are treatment-related
- All serious TEAEs
- All serious TEAEs that are treatment-related
- All unsolicited TEAEs leading to discontinuation from participation in the study
- All unsolicited Severe TEAEs
- All unsolicited Severe TEAEs that are treatment-related
- All unsolicited TEAEs that are medically-attended
- All unsolicited medically-attended TEAEs that are treatment-related

- All AESIs of myocarditis and/or pericarditis
- All AESIs other than myocarditis and/or pericarditis
- All AESIs that are treatment-related

### **6.3.2. Solicited Adverse Reactions**

An AR is any AE related to the IP injection. **Solicited Adverse Reactions**, i.e., reactogenicity, refers to selected signs and symptoms occurring after injection administration during a specified post-injection follow-up period (the day of injection and 6 subsequent days). The occurrence and intensity of the solicited ARs are recorded by subject in eDiary with some occasions that may be captured in **Solicited Adverse Reaction (SAR) eCRF** page. If a solicited local or systemic AR continues beyond 7 days after injection, the participant will be prompted to capture solicited local or systemic AR in the eDiary until resolution.

The following local ARs will be solicited by the eDiary: pain at injection site, erythema (redness) at injection site, swelling (hardness) at injection site, localized axillary swelling or tenderness ipsilateral to the injection arm, and groin or underarm swelling or tenderness ipsilateral to the side of injection.

The following systemic ARs will be solicited by the eDiary: headache, fatigue, myalgia (muscle aches all over the body), arthralgia (aching in several joints), nausea/vomiting, fever, chills, irritability/crying, sleepiness, and loss of appetite.

The number and percentage of participants who reported solicited local AR, solicited systemic AR and any SAR, regardless of local or systemic, during the 7-day follow-up period after the IP injection will be tabulated by treatment group, toxicity grade, age group and day of reporting (Day 1 through Day 7). A two-sided 95% CI using the Clopper-Pearson method will be provided for the percentage of participants. The tables will be generated for all SARs both within or persisting beyond 7 days of injection separately.

The AR with the same selected signs and symptoms occurring 7 days after IP injection is called “delayed SAR”, whose incidence will be also summarized.

The onset of the SAR is defined as the day after the IP injection at which the respective SAR first occurred. The number and percentage of subjects with onset of SAR will be summarized by treatment group, day of reporting (Day 1 through Day 7). The tables will be generated for all SARs both within or persisting beyond 7 days of injection separately.

The SAR duration will be summarized for SARs by treatment group, within the 7 days of the IP injection and those persisting beyond 7 days separately. The duration of SAR in days will be calculated from the first to the last day when the solicited AR occurred within the 7 days of injection including the day of injection.

SARs collected on eDiary, along with those collected on reactogenicity aCRF, will be provided in a listing with the maximum grade from eDiary and aCRF. All SARs that persist beyond 7 days after IP injection will be listed separately.

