### **7.3.1. Use of Electronic Diaries**

At the time of consent, the participants must confirm they will be willing to complete an eDiary using either an application downloaded to their smartphone or using a device that will be provided at the time of enrollment. Before enrollment on Day 1, the participant will be instructed to download the eDiary application or will be provided an eDiary device to record solicited ARs ([Section 7.4.3](#)) on Day 1.

On Day 1 (vaccination day), participants will be instructed on thermometer usage to measure body temperature, ruler usage to measure injection site erythema and swelling/induration

(hardness), and self-assessment for localized axillary swelling or tenderness on the same side as the injection arm.

On Day 1 (vaccination day), participants will record data into the eDiary starting approximately 30 minutes after the injection under supervision of the study site staff to ensure successful entry of assessments. The study site staff will perform any retraining as necessary. Participants will continue to record data in the eDiary after they leave the study site, preferably in the evening and at the same time each day, on the day of injection and for 6 days following injection.

Participants will record the following data in the eDiary:

- Solicited local and systemic reactogenicity ARs, as defined in [Section 7.4.3](#), that occur on the day of vaccination and during the 7 days after vaccination (ie, the day of injection and 6 subsequent days). Any solicited AR that is ongoing beyond Day 7 will be reported in the eDiary until it has resolved, and not to exceed 28 days after vaccination. Adverse reactions recorded in the eDiary beyond Day 7 should be reviewed by the study site staff either during the next scheduled telephone call or at the next study site visit.
- Daily oral body temperature measurement should be performed at approximately the same time each day using the thermometer provided by the study site. If body temperature is taken more than once in a given day, only the highest temperature reading should be recorded.
- Other measurements, as applicable, for solicited local ARs (injection site erythema and swelling/induration) will be performed using the ruler provided by the study site.
- Any medications taken to treat or prevent pain or fever on Day 1 or for the next 6 days.

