#### **7.4.3.      Solicited Adverse Reactions**

The term “reactogenicity” refers to the occurrence and intensity of selected signs and symptoms (ARs) occurring after IP injection. The eDiary will solicit daily participant reporting of ARs using a structured checklist ([Section 7.3.1](#)). Participants will record such occurrences in an eDiary during the 7 days after vaccination (ie, the day of injection and 6 subsequent days).

Severity grading of reactogenicity will occur automatically based on participant entry into the eDiary according to the grading scales presented in [Table 5](#) modified from the Toxicity Grading Scale for Healthy Adult and Adolescent Volunteers Enrolled in Preventive Vaccine Clinical Trials ([DHHS 2007](#)).

If a solicited local or systemic AR continues beyond 7 days after vaccination, the participant will be prompted daily to capture solicited local or systemic AR in the eDiary until resolution.

Adverse reactions recorded in eDiaries beyond Day 7 should be reviewed by the study staff either via phone call or at the next study visit. All solicited ARs (local and systemic) will be considered causally related to vaccination.

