Fever (oral)	< 38.0°C < 100.4°F	38.0 – 38.4°C 100.4 – 101.1°F	38.5 – 38.9°C 101.2 – 102.0°F	39.0 – 40.0°C 102.1 – 104.0°F	> 40.0°C > 104.0°F

Note: Events listed above but starting > 7 days after study injection will be recorded on the AE CRF. Causality for each event will be determined per assessment by the investigator.

Any solicited AR that meets any of the following criteria must be entered into the participant's source document and must also be recorded by the study site staff on the solicited AR page of the participant's eCRF:

- Solicited local or systemic AR that results in a visit to a healthcare practitioner (HCP), to be recorded as an MAAE ([Section 7.4.4](#))
- Solicited local or systemic AR leading to the participant withdrawing from the study or the participant being withdrawn from the study by the investigator (AE leading to withdrawal)

- Solicited local or systemic AR lasting beyond 7 days post-injection
- Solicited local or systemic AR that otherwise meets the definition of an SAE

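### The only duration rule for solicited reactions, read literally, stops at Day 7, so the planned duration table for reactions persisting beyond 7 days would only restate onset day

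*SAP*

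**What the plan says.** SAP 6.3.2 summarises the duration of solicited adverse reactions by treatment group, "within the 7 days of the IP injection and those persisting beyond 7 days separately". The next sentence gives the rule: duration in days is "calculated from the first to the last day when the solicited AR occurred within the 7 days of injection including the day of injection". The SAP has no other duration rule for these reactions. The general conventions (SAP 6.1) and the AE date rules (SAP 9.4) do not supply one, and Protocol 8.5.3 with Table 7 plans no duration analysis to fall back on.

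The same SAP section treats persisting reactions as a class of their own elsewhere. For incidence, and again for onset day (Day 1 to Day 7), it says: "The tables will be generated for all SARs both within or persisting beyond 7 days of injection separately". It also provides a listing: "All SARs that persist beyond 7 days after IP injection will be listed separately".

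Data after Day 7 are collected. In the SAP, for a reaction that continues, "the participant will be prompted to capture solicited local or systemic AR in the eDiary until resolution". Protocol 7.4.3 agrees: "the participant will be prompted daily to capture solicited local or systemic AR in the eDiary until resolution". Sites must also enter on the solicited AR page of the eCRF any "Solicited local or systemic AR lasting beyond 7 days post-injection". Protocol 7.3.1 adds a limit that the other two places lack: a reaction "ongoing beyond Day 7 will be reported in the eDiary until it has resolved, and not to exceed 28 days after vaccination".

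**The concern.** A duration summary for persisting reactions is useful only if it shows how long they go on after Day 7. The one rule given takes both the first and the last day from inside the 7-day window. For a reaction that runs through Day 7 the end day is then fixed, and only the start day can vary. The table would carry the heading of a duration summary and the content of an onset summary.

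The study informs dose selection, and reactogenicity is part of the primary objective in both parts. Differences between groups in how many reactions persist would still be visible in the incidence tables. Differences in how long they persist would not appear in the one table planned to show them.

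**Working it through.** The plan states no figure to reproduce, so the check applies the rule to every possible case.

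**Inputs**
- Solicited window: day of injection plus 6 days, that is Day 1 to Day 7 (SAP 6.3.2).
- Onset day *s*: 1 to 7.
- Last day with the reaction *e*: 8 or later for a persisting reaction.
- Upper limit on *e*: 28 days after vaccination in Protocol 7.3.1; no limit stated in Protocol 7.4.3 or SAP 6.3.2.

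**Formulas**
- Literal rule: min(*e*, 7) − *s* + 1. For *e* ≥ 8 with the reaction present on Day 7, this is 8 − *s*.
- Without the cap: *e* − *s* + 1.
- Shortfall for *e* ≥ 8: (*e* − *s* + 1) − (8 − *s*) = *e* − 7, whatever the onset day.

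**Literal result by onset day.** Onset on Day 1, 2, 3, 4, 5, 6, 7 gives 7, 6, 5, 4, 3, 2, 1 days. Each onset day gives exactly one duration, so the table holds the same information as the onset table.

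**Examples**

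| Onset day | Last day | Literal | Uncapped | Shortfall |
|---|---|---|---|---|
| 1 | 8 | 7 | 8 | 1 |
| 2 | 10 | 6 | 9 | 3 |
| 7 | 12 | 1 | 6 | 5 |
| 2 | 20 | 6 | 19 | 13 |
| 1 | 28 | 7 | 28 | 21 |
| 7 | 28 | 1 | 22 | 21 |

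The largest shortfall is 28 − 7 = 21 days if the 28-day limit is counted with injection as Day 1, and 29 − 7 = 22 days if it means Day 29. If collection really runs until resolution, there is no upper bound.

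**Effect on a group comparison (invented values).** Take two groups of five persisting reactions, both with onset days 1, 1, 2, 2, 3.
- Last days 9, 10, 9, 10, 11: uncapped durations 9, 10, 8, 9, 9; median 9.
- Last days 18, 20, 22, 19, 21: uncapped durations 18, 20, 21, 18, 19; median 19.
- Literal durations in both groups: 7, 7, 6, 6, 5; median 6.

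A 10-day difference in medians disappears.

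**Within-7-days table.** Here the resolution day still varies (onset on Day 1 can give 1 to 7 days), so the cap does no harm.

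**The case against.** The strongest reply is that the phrase about the 7 days may select which reactions count, by when they start, and not limit the end day. The documents do classify by start: an event of a solicited type that begins after the window is unsolicited (Protocol 7.4.1), and the SAP has a separate name for later occurrences. A Day 7 cap would also empty the separate summary promised in the sentence before. This may well be what was intended. But the text does not say it, and the preceding sentence uses the 7-day phrase as the opposite of persisting beyond 7 days. A third reading, that the rule covers only the within-window table, leaves the persisting table with no rule. All three readings need the same added sentence.

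Four smaller points stand in part:
- The exact link to onset day assumes that the reaction is present on Day 7. An intermittent reaction absent that day could score less, though never more than 7. Persisting beyond 7 days ordinarily implies presence on Day 7.
- The group illustration shows what can happen, not what is likely.
- Two places that omit the 28-day limit do not deny it, so an unbounded shortfall is conditional on taking them at their word.
- The output is supplementary and no hypotheses are tested, which limits the consequence.

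**Conclusion.** The concern holds. Followed as written, the rule gives every reaction that continues through Day 7 a duration of 8 minus its onset day, and understates it by the last reported day minus 7: from 1 day up to 21 days for a last report on Day 28. This rests on the literal reading and on the reaction being present on Day 7. If the uncapped reading was meant, the defect is one of wording, but a programmer could not tell that from the SAP.

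The consequence is limited. The primary endpoints of frequency and grade (SAP 3.1.1 and 3.2.1), the incidence tables for persisting reactions and the separate listing are not affected. How many participants would be concerned is unknown. The only duration figure in the documents, for mRNA-1273 in Protocol 1.3.2, is a median of 1 to 3 days for most reactions, so persisting cases may be few. The correction should be made, but it does not threaten the main results.

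**What to change.** In SAP 6.3.2, state that for solicited reactions with onset on Day 1 to Day 7, duration is the last reported day with the reaction (eDiary or solicited AR eCRF page) minus the first day plus 1, with no cap at Day 7. Flag reactions still ongoing when eDiary collection ends, because their durations are only minimum values.

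The same sentence should say which source prevails if eDiary and eCRF differ, since Protocol 7.3.1 makes the eDiary the sole source document for solicited reactions. It should also say whether symptom-free days between first and last day count.

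Reconcile the end of eDiary collection between Protocol 7.3.1 (28-day limit) and Protocol 7.4.3 and SAP 6.3.2 (until resolution only), and state whether the limit means Day 28 or Day 29. This decides which reactions are flagged as ongoing.

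The cost is a short SAP clarification, a small programming change and the reconciliation of the collection wording. No new data are needed. Reported durations for persisting reactions will be longer than under the literal rule.

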### 6.3.3. Clinical Laboratory Evaluations

No routine safety laboratory assessments are planned for this study.

A point-of-care urine pregnancy test will be performed at Day 1 before vaccination. At any time, a pregnancy test either via blood or point-of-care urine can be performed, at the discretion of the investigator. If postmenopausal status is not documented in a female participant's medical records, a follicle-stimulating hormone (FSH) test to confirm may be performed at the Screening Visit, as necessary and at the discretion of the investigator.

A by-subject listing will be provided for pregnancy tests with positive results.

### 6.4. Immunogenicity Analysis

The analyses of immunogenicity will be based on the PPIS and PPIS-Neg and will be performed by treatment group as defined in [Section 6.1](#).

The geometric mean titer (GMT) and geometric mean (GM) level will be calculated using the following formula:

$$10^{\left\{ \frac{\sum_{i=1}^n \log_{10}(t_i)}{n} \right\}}$$

where  $t_1, t_2, \dots, t_n$  are  $n$  observed immunogenicity titers or levels.

The geometric mean fold-rise (GMFR) measures the changes in immunogenicity titers or levels within subjects. It will be calculated using the following formula:

$$10^{\left\{ \frac{\sum_{i=1}^n \log_{10}\left(\frac{v_{ij}}{v_{ik}}\right)}{n} \right\}} = 10^{\left\{ \frac{\sum_{i=1}^n \log_{10}(v_{ij}) - \log_{10}(v_{ik})}{n} \right\}}$$

where, for  $n$  subjects,  $v_{ij}$  and  $v_{ik}$  are observed immunogenicity titers or levels for subject  $i$  at time points  $j$  and  $k$ ,  $j \neq k$

#### 6.4.1. Immunogenicity Assessments

Blood samples for immunogenicity assessments will be collected at the time points indicated in the SoE. The following immunogenicity will be measured:

- The levels of Serum bAb, against SARS-CoV-2 and its variants, as measured by ligand-binding assay specific to the SARS-CoV-2 S protein, the S protein RBD, Nucleocapsid protein and NTD
- The Titers of Serum nAb, against SARS-CoV-2 and its variants, as measured by pseudo-virus neutralization assays
- Serologic markers for SARS-CoV-2 infection as measured by antinucleocapsid antibodies detected by immunoassay at the baseline (Day 1) and scheduled post-baseline timepoints

#### 6.4.2. Analysis for the Primary Immunogenicity Objective

For Part A and Part B, PPIS-Neg will be used as primary analysis set. Sensitivity analyses may be performed using PPIS and a subset of PPIS-Neg only including subjects with no virologic or serologic evidence of SARS-CoV-2 infection on or before Day 29 or Day 91, i.e., RT-PCR results are not positive up to Day 29 or Day 91 and negative bAb specific to SARS-CoV-2 nucleocapsid on or before Day 29 or Day 91. The comparison of immunogenicity between the different vaccines is descriptive.

Part A:

For the primary immunogenicity endpoints of levels of serum nAb and bAb against SARS-CoV-2 prototype virus strain and its variant strains including B.1.351, immune response of each treatment group will be assessed with respect to mRNA-1273 CCI booster dose.

An analysis of covariance (ANCOVA) model will be employed to compare immune response of each treatment group with that of mRNA-1273 CCI booster dose. Day 29 serum bAb or nAb (against prototype virus strain or the variant strain) will be included in the model as a dependent variable and a treatment group variable (mRNA-1283 at each dose level, mRNA-1283.211 at each dose level, and mRNA-1273 CCI) will be included

as the fixed effect. The model will also adjust for age group (18-55, and  $\geq$ 56 years of age) and the pre-booster baseline value.

The GMT or GM level will be estimated by the geometric least square mean (GLSM) from the model for each treatment group and its corresponding 95% CI will be provided.

The GMR (ratio of GMTs or GM levels) for each treatment group with respect to mRNA-1273 CCI booster dose will be estimated by the ratio of GLSM from the model. The 95% CI of the ratio of GLSM will be provided to assess the between-group difference (each treatment group against mRNA-1273 CCI booster dose) in immune response against the prototype strain (or variant strains).

The primary immunogenicity endpoints of Part A will also be assessed by the vaccine seroresponse against SARS-CoV-2 prototype virus strain and against variant strains including B.1.351. Vaccine seroresponse at a time point is defined by an increase of SARS-CoV-2 specific bAb level or nAb titer to at least 4xLLOQ if the baseline is below the lower limit of quantification (<LLOQ), or a 4-fold or greater rise if pre-booster  $\geq$  LLOQ.

Two types of baselines for Part A will be employed to compute the seroresponse:

- 1) Pre-vaccination (Pre-Dose 1 of the primary series)
- 2) Pre-booster

Seroresponse based on pre-vaccination is defined as  $\geq$  4\*LLOQ for subjects with negative SARS-CoV-2 status at their pre-vaccination baseline. For this study, subjects SARS-CoV-2 status at pre-booster baseline will be used to impute their SARS-CoV-2 status pre-vaccination baseline. If the participant tests negative at pre-booster, the serum Ab value of the pre-vaccination baseline will be imputed with LLOQ, otherwise, For subjects with positive SARS-CoV-2 status at pre-booster, their seroresponse based on pre-vaccination baseline will be set to missing.

The SRR at Day 29 will be summarized for each treatment group with its 95% CI calculated with the Clopper-Pearson method. The difference of SRRs at Day 29 for mRNA-1283 at each dose level, mRNA-1283.211 at each dose level compared with mRNA-1273 will be provided with its 95% CI with the Miettinen-Nurminen method.

Part B:

Similar analysis methods will be used to analyze immunogenicity data for Part B. An ANCOVA model will be used to compare immune response between treatment group (██████████ mRNA-1283.529). Day 29 antibody titers against B.1.1.529 will be included in the model as a dependent variable and treatment group variable (mRNA-1283.529 at each dose level) will be included as fixed effect, adjusting for age group (< 56,  $\geq$  56) and the pre-booster baseline Ab value. The GMT will be estimated by the GLSM from the model for each group and corresponding 95% CI will be provided. The ratio of GMTs for CCI mRNA-1283.529 with respect to CCI mRNA-1283.529 booster dose will be estimated by the ratio of GLSM from the model. The 95% CI for the ratio of GLSM will be provided to assess the between-group difference in immune response against B.1.1.529.

SRR against B.1.1.529 at Day 29 will be summarized for each mRNA-1283.529 dose level with its 95% CI calculated using the Clopper-Pearson method. The difference of SRRs at Day 29 between two dose levels will also be calculated with 95% CI using the Miettinen-Nurminen method.

For Part B, seroresponse will be based on both pre-vaccination and pre-booster baseline as well. The derivation rule is the same as described in Part A.

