### **5.5. Per-Protocol Immunogenicity Set – Pre-booster SARS-CoV-2 Negative (PPIS-Neg)**

The PPIS-Neg consists of participants who are in PPIS and are pre-booster SARS-CoV-2 negative, defined as no virologic or serologic evidence of SARS-CoV-2 infection on or before booster, i.e., RT-PCR result is not positive if available at pre-booster and a negative bAb specific to SARS-CoV-2 nucleocapsid on or before booster. The PPIS-Neg will be used as the analysis set for the primary analyses of immunogenicity.

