## 6. Statistical Analysis

### 6.1. General Considerations

Please refer to Table 8 in the protocol for Schedule of Events (SoE).

The following follow-up periods for safety analyses and Concomitant Medications will be used:

- Overall follow-up period (throughout the study): from the day of the IP injection (Day 1) to the earliest date of (study completion, discontinuation from the study, or death)
- Up to 28 days follow-up period: from the day of the IP injection (Day 1) to the earliest date of (the day of the IP injection and 27 subsequent days, discontinuation from the study, or death)
- After 28 days follow-up period: from the 28 days after the IP injection to the earliest date of (study completion, discontinuation from the study, or death)
- 7-day follow-up period: from the day of the IP injection (Day 1) to the earliest date of (Day 7 after the IP injection, discontinuation from the study, or death)

**Continuous variables** will be summarized using the following descriptive summary statistics: the number of subjects (n), mean, standard deviation (SD), median, minimum (min), and maximum (max).

**Categorical variables** will be summarized using counts and percentages.

**Baseline value**, unless specified otherwise, is defined as the most recent non-missing measurement (scheduled or unscheduled) collected before the dose of IP in this study.

For the summary statistics of all numerical variables unless otherwise specified, the display precision will follow programming standards. Please see [Appendix A](#) for variable display standards.

When count data are presented, the percentage will be suppressed when the count is zero in order to draw attention to the non-zero counts. A row denoted “Missing” will be included in count tabulations where specified on the shells to account for dropouts and missing values. The denominator for all percentages will be the number of subjects in the treatment group within the analysis set of interest, unless otherwise specified.

**End of Study** (EoS) for the participants is defined as any of completion of the study if the participant has completed all phases of the study including the last scheduled procedure as shown in the SoE (Table 8 in the protocol), discontinuation of study due to any reason, death, and termination of the trial by the Sponsor.

**Pre-booster SARS-CoV-2 status** is determined by using virologic and serologic evidence of SARS-CoV-2 infection on or before Day 1 (pre-booster).

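### Does the Day 29 seroresponse rate need one named main baseline, given that the imputed pre-vaccination version can count a participant with no rise after the study vaccine?

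*SAP*

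**What the plan says.** Protocol 8.5.4.1 makes the Day 29 seroresponse rate one of the ways the primary immunogenicity endpoints are assessed and leaves its definition to the SAP.

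SAP 6.4.2 first gives a general rule. A participant responds by reaching at least 4×LLOQ when the baseline is below LLOQ, "or a 4-fold or greater rise if pre-booster" is at or above LLOQ. It then adds: "Two types of baselines for Part A will be employed to compute the seroresponse". The first is labelled "Pre-vaccination (Pre-Dose 1 of the primary series"); the second is pre-booster. Part B follows suit: "For Part B, seroresponse will be based on both pre-vaccination and pre-booster baseline as well".

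No sample from before the primary series is used, so the first baseline is imputed. Pre-booster infection status stands in for pre-vaccination status. For negatives, "If the participant tests negative at pre-booster, the serum Ab value of the pre-vaccination baseline will be imputed with LLOQ". For positives, "their seroresponse based on pre-vaccination baseline will be set to missing".

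The SAP then describes the Day 29 SRR (Clopper-Pearson interval) and its between-group difference (Miettinen-Nurminen interval) without saying which baseline is meant or which leads.

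Two other provisions bear on the point. SAP 6.1 sets a default baseline which, "unless specified otherwise, is defined as the most recent non-missing measurement (scheduled or unscheduled) collected before the dose of IP in this study". SAP 5.5 fixes the population: "The PPIS-Neg will be used as the analysis set for the primary analyses of immunogenicity".

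**The concern.** The study asks what a further dose adds in people who have already had mRNA-1273, and the results inform dose selection. A responder definition that ignores the Day 1 titre appears to miss that question. Antibody left over from earlier doses can make someone a responder even if the study vaccine did nothing.

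If Day 1 titres sit well above LLOQ, nearly everyone in every arm passes the threshold. The rate then approaches a ceiling and loses its ability to separate dose levels or to separate a candidate from mRNA-1273. Among negatives the pre-vaccination rate can never be the lower of the two, so the choice of version works in one direction. With neither named as main, the higher and flatter rate could be quoted as the primary result.

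The same version is also missing for pre-booster positives. It adds essentially nothing in the PPIS sensitivity analysis and is unavailable in the positive subgroup of SAP 6.5.

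**Working it through.** **Inputs from the documents.** Both seroresponse rules and the LLOQ imputation (SAP 6.4.2); PPIS-Neg as primary set (SAP 5.5); up to 70 participants per group (SAP 4.2). The documents give no LLOQ, titre, SD or expected SRR, so there is no planned figure to reproduce.

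**Step 1: what each rule reduces to.** Work in units of LLOQ, with b the Day 1 value and d the Day 29 value, for pre-booster negatives.

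- Pre-vaccination version: respond if d ≥ 4. The imputed baseline is the constant 1, so b drops out.
- Pre-booster version: respond if d ≥ 4 when b < 1, or if d/b ≥ 4 when b ≥ 1.

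| b → d | Fold | Pre-vaccination | Pre-booster |
|---|---|---|---|
| 0.5 → 4 | 8 | yes | yes |
| 8 → 8 | 1 | yes | no |
| 32 → 8 | 0.25 | yes | no |
| 16 → 64 | 4 | yes | yes |

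**Step 2: nesting.** If b < 1 the rules are identical. If b ≥ 1 and d/b ≥ 4, then d ≥ 4b ≥ 4. Every pre-booster responder is therefore a pre-vaccination responder. The two rates differ by exactly the share with b ≥ 1, d ≥ 4 and d/b < 4.

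**Step 3: illustrative size.** Assume lognormal titres with log10 SD 0.5 at Day 1 and 0.3 for the fold rise, the rise independent of the Day 1 titre. With Day 1 median m and median fold rise g, the pre-vaccination rate is Φ{[log10(m) + log10(g) − log10(4)] / √(0.5² + 0.3²)}, where the denominator is 0.583. The pre-booster rate uses the same inputs, split at b = 1.

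Example: m = 4, g = 8 gives Φ(0.903/0.583) = Φ(1.55) = 94%; g = 16 gives Φ(1.204/0.583) = Φ(2.07) = 98%. The gap is 4 points. The pre-booster rates are 81% and 96%, a gap of 15 points.

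| Day 1 median (×LLOQ) | SRR with no booster effect: pre-vaccination / pre-booster | Gap, 16- vs 8-fold arms: pre-vaccination / pre-booster (points) |
|---|---|---|
| 0.5 | 6% / 1% | 20 / 22 |
| 1 | 15% / 1% | 15 / 20 |
| 4 | 50% / 2% | 4 / 15 |
| 16 | 85% / 2% | 0.4 / 14 |

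With 70 per arm at m = 4 and expected counts rounded to whole participants, the Miettinen-Nurminen intervals are 4 points (−3 to 13) for 69 vs 66 responders, and 14 points (4 to 26) for 67 vs 57.

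**Step 4: what else is reported.** SAP 6.4.3 tabulates the proportion with a fold rise of at least 4 from baseline, which by the SAP 6.1 default is the value before the study vaccine. For b ≥ 1 this is the same criterion as the pre-booster seroresponse. For b < 1 the value is set to 0.5×LLOQ (SAP 6.1), so a 4-fold rise means d ≥ 4 × 0.5 = 2 rather than d ≥ 4; the two differ only for Day 29 values from 2 up to 4×LLOQ. The SAP also plans GMFR, reverse cumulative distribution plots, and geometric mean ratios from an ANCOVA adjusted for the pre-booster value. All of these are free of the imputed baseline.

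**The case for a change.** The best case for a change is that SAP 6.4.2 is the only place where the definition can be settled, and it leaves a primary measure in two unranked versions. The SAP 6.1 default does not settle it, because it gives way where another baseline is specified, and 6.4.2 specifies both. Only the pre-booster version is defined for negatives and positives alike. Naming it would cost one sentence and some table labels.

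The reading of the text stands, and so does the point that the pre-vaccination version does not isolate the study vaccine. What falls away is the consequence. Both versions are committed to in advance for both parts, so neither can be added or dropped after results are seen. The pre-vaccination baseline is described for what it is, a cumulative measure, and counting someone without a recent rise is a property of that measure rather than an error. Leaving it missing for positives is reasonable, since their pre-vaccination status and titre are unknown. PPIS analyses are optional, and only selected immunogenicity analyses are planned by subgroup.

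Which version should lead is also open to argument. SAP 6.1 may cap values at the ULOQ, so a participant with a very high Day 1 titre may be unable to show a 4-fold rise; the pre-vaccination version avoids that limit.

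A smaller point concerns participants with no pre-booster RT-PCR result. SAP 5.5 admits them to PPIS-Neg, while SAP 6.1 asks for a negative test. A Day 1 swab is scheduled for everyone, so this is a wording mismatch that should touch few participants, and analysts would apply the SAP 5.5 definition within that set.

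**Conclusion.** The description is accurate but the plan need not change. The two rates answer two different questions, both are prespecified, and a reader can tell them apart by the baseline each uses. The general rule's own clause and the default baseline already lean towards pre-booster, so analysts have a sensible lead version to hand. No hypothesis is tested and SAP 6.4.2 calls the comparison between vaccines descriptive, so no error rate or formal decision depends on which rate is listed first. Where the choice would matter most, with Day 1 titres well above LLOQ, the planned 4-fold-rise table is almost the same quantity as the pre-booster SRR, and GMFR and the adjusted ratios carry the booster effect as well.

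Ranking the versions would change no estimate, interval or analysis set. Labelling each SRR table with its baseline is ordinary practice at the table-shell stage.

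The sizes above are illustrations: the titres, SDs and independence of rise from Day 1 level are all assumed. On those assumptions the versions largely agree on between-arm differences when Day 1 medians are below LLOQ (20 against 22 points at 0.5×LLOQ) and part company above it (4 against 15 points at 4×LLOQ). Agreement on the level of the rate is looser: at a median of 0.5×LLOQ, an arm with a 4-fold rise would show 30% against about 22%.
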